# Development and internal validation of models to predict time-to-event for major medical complications within 30-days after planned colectomy: a retrospective population cohort study

# Introduction

Planned (elective or time sensitive) colectomy are performed for indications including cancer, inflammatory bowel disease (IBD), and diverticulitis (1,2). After colectomy, patients are at risk of a variety of major medical complications, including pneumonia, myocardial infarction (MI), cerebral vascular event (CVA), venous thromboembolism (VTE), acute renal failure (ARF), and sepsis (2,3). However, different complications tend to happen at different times after surgery. Accurate risk prediction, not only whether a complication may occur in a patient, but also when, is crucial for patient education, monitoring, and disposition planning. While several studies have explored the incidence and binary risk prediction for major complications after surgeries (1–3), there has been scarce literature on time-to-complication prediction modeling in recent population cohort data.

# Objectives

- Develop and internal validate Cox proportional hazards models to predict time-tocomplication for each individual major medical complication captured in the American College of Surgeons National Surgical Quality Improvement Program (NSQIP) dataset (pneumonia, myocardial infarction (MI), cerebral vascular event (CVA), venous thromboembolism (VTE), acute renal failure (ARF), and sepsis) or adverse outcomes (mortality, readmission), that started within 30-days after elective colectomy.
- 2. Develop and internal validate machine learning models to predict time-tocomplication for major medical complications and adverse outcomes (same as in objective 1) within 30-days after elective colectomy in NSQIP. The best machine learning model for each complication will be compared to the Cox proportional hazards model in terms of discrimination, and calibration.

# Methods

Following approval from the University of British Columbia Clinical Research Ethics Board with waived informed consent, we will conduct a time-to-event survival analysis in a retrospective cohort using NSQIP®, a prospectively-collected multicentre dataset with more than 150 clinical variables within 30 days after surgery (4). This dataset includes information on whether the patient was diagnosed with major complications (in- or out-of-hospital) as well as the number of postoperative days to the diagnoses of complications, as defined by a standardized criteria within the NSQIP operations manual (4). The general dataset will be linked with the NSQIP® Procedure Targeted Colectomy dataset, which contains additional colectomy-specific variables. The study will be pre-registered prior to data analysis (Clinicaltrials.gov) and reported according to the Transparent reporting of a multivariable prediction model for individual prognosis or diagnosis (TRIPOD) guidelines and Guidelines for Developing and Reporting Machine Learning Predictive Models in Biomedical Research (5).

Protocol Version #2

## **Study Population**

The study will include all patients who are 18 years or older undergoing elective colectomy, whose data has been collected in the NSQIP® Procedure Targeted Colectomy dataset from 2014-2019, inclusively. The estimated sample size is approximately 130,000 patients.

We will exclude patients with American Society of Anesthesiologists (ASA) Physical Status (PS) V (defined as "5-Moribund") (ASA PS 6 - organ donation is not included within NSQIP). We will also exclude patients who are undergoing urgent or emergency surgery, or have indication for colectomy consisting of "Acute diverticulitis", "Enterocolitis (e.g. C. Difficile)", and "Volvulus" due to the non-elective nature of these pathologies. Patients with disseminated cancer, wound infection (i.e. potentially recent surgery), systemic sepsis, or ventilator-dependence preoperatively will also be excluded.

## Model Prediction Endpoints

We will create a distinct time-to-event prediction model for each of the following new postoperative complications or adverse outcomes within 30 days postoperatively:

- Major medical complications: pneumonia, myocardial infarction (MI), cerebral vascular event (CVA), venous thromboembolism (VTE), acute renal failure (ARF), and sepsis or septic shock
- Adverse outcomes: mortality, readmission

The definitions of the complications, outcomes, and time-to-complication date criteria collected from NSQIP variables are included in Appendix 1 (Data Extraction Form).

## Candidate predictors

To predict time-to-complication, we selected candidate predictors from the NSQIP variables based on literature and clinical experience, and obtained consensus within our multidisciplinary team. For generalizability and future external validation, we selected predictors that are routinely collected in hospital electronic health records (EHRs) such as at our institution whenever possible. Candidate predictors are as follows (please see Appendix 1 for detailed definitions):

- Age, sex, race, body mass index (BMI)
- ASA, diabetes, smoker within one year preoperatively, severe obstructive chronic pulmonary disease (COPD), ascites, congestive heart failure (CHF), hypertension on medications, preoperative renal failure (acute renal failure, dialysis, and/or glomerular filtration rate (GFR) <60 based on preoperative creatinine), preoperative functional status, dyspnea, coagulopathy
- Steroid and/or immunosuppressant use preoperatively
- Chemotherapy within 90 days preoperatively
- Primary indication for colectomy (recategorized as):
  - Cancer
  - Non-malignant polyp
  - Inflammatory bower disease (IBD)
  - Diverticulitis
  - Bleeding
  - Other
- Surgical approach: minimally invasive vs. open
- Total operation time
- Use of regional anesthesia as an additional anesthetic technique (epidural, peripheral, spinal)
- Wound classification (end of surgery)

Nov 9, 2021 Protocol Version #2

Ke et al.

For the two models to predict time-to-event for adverse outcomes (mortality and readmission), we will perform sensitivity analysis to determine whether including the occurrence of any major complications (pneumonia, myocardial infarction (MI), cerebral vascular event (CVA), venous thromboembolism (VTE), acute renal failure (ARF), and sepsis) as individual predictors improve discrimination and calibration.

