  - Cohort characteristics will be stratified by mortality, by each complication and by derivation vs. validation sets (please see list below). Continuous variables will be presented as mean (standard deviation) and median (IQR) for parametric and nonparametric data, respectively. Categorical variables will be

4

presented as frequency (%). For comparison amongst groups, ANOVA will be used for parametric data, Kruskal-Wallis for nonparametric data, and Chisquare tests for categorical data. Standardized mean difference will be presented. Exploratory visualizations will be performed.

- Distribution of time to complication data (time to any complication, and time to each complication): failure curves, i.e. plotting the 1-S(t) (survival function) to determine the risk of complication daily within 30 days
- Exploratory analysis for complications that tend to occur concurrently or are associated with each other
- 3. Model building
  - Models will be created using the entire dataset and using bootstrap validation
    - Individual models will be built for each outcome.
    - Assumptions for the Cox model will be checked prior to model building, including but not limited to:
      - 1. Proportionality: visual inspection of the Kaplan-Meier curves, Log Log S(t) test, Schoenfeld residuals. If these assumptions hold, we will use the Cox proportional hazards (CPH) modeling; if not, we will use the accelerated failure time (AFT) modeling.
      - 2. Competing risk: complications are assumed to be independent from each other. If mortality is >10%, it will be modeled as a competing risk (however, we do not anticipate mortality to be >10% for elective colectomy).
    - Sensitivity analyses
      - 1. After examining the temporal distributions of events, we may include complications that tend to happen earlier as predictors for complications that happen later, and may be related to earlier complications
      - 2. For the two models to predict time-to-event for adverse outcomes (mortality and readmission), we will perform sensitivity analysis to determine whether including the occurrence of major complications (pneumonia, myocardial infarction (MI), cerebral vascular event (CVA), venous thromboembolism (VTE), acute renal failure (ARF), and sepsis) as predictors improve discrimination and calibration
      - 3. Restricted cubic splines for continuous predictors (age, BMI, duration of surgery) to explore non-linear relationships

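### The model for new acute renal failure keeps patients already on dialysis in its risk set and assigns them the GFR <60 risk

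*Combined protocol and SAP*

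**What the plan says.** All references are to the combined protocol and SAP.

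- **Model Prediction Endpoints.** Each endpoint has its own model and must be a new event: "We will create a distinct time-to-event prediction model for each of the following new postoperative complications or adverse outcomes within 30 days postoperatively". ARF is one of eight endpoints. Definitions are deferred: "time-to-complication date criteria collected from NSQIP variables are included in Appendix 1 (Data Extraction Form".
- **Study Population.** The preoperative conditions that lead to exclusion are these: "Patients with disseminated cancer, wound infection (i.e. potentially recent surgery), systemic sepsis, or ventilator-dependence preoperatively will also be excluded". Preoperative ARF and dialysis are not among them.
- **Candidate predictors.** One predictor covers three renal states: "preoperative renal failure (acute renal failure, dialysis, and/or glomerular filtration rate (GFR) <60 based on preoperative creatinine". The plan therefore expects such patients in the cohort.
- **Statistical Analysis, item 3 (model building).** "Models will be created using the entire dataset and using bootstrap validation". No at-risk set is defined for any single outcome, and none of the four sensitivity analyses separates or removes patients with preoperative ARF or dialysis.
- **Statistical Analysis, item 1 (preprocessing).** A missing complication value is coded as no complication.
- **Statistical Analysis, item 4 (model evaluation).** The measures are AUROC, pseudo R-squared, scaled Brier score and calibration plots. No calibration by subgroup is named.

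**The concern.** A model for a new event should be fitted in patients who can have it. Followed as written, the plan keeps dialysis patients in the ARF risk set for 30 days with no possible event, in the same predictor category as patients with GFR <60. One coefficient then averages a group whose hazard is zero with a group whose hazard is presumably raised. Neither the Cox model nor a machine learning model can tell the two apart through this predictor.

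Two things are at stake. Patients with GFR <60 who can have the event would get a risk that is somewhat too low, and ineligible patients would get a positive risk for an event they cannot have. The planned evaluation may not show this, because the two errors offset each other within the predictor-positive group and average calibration there can look sound. The Introduction says predictions are meant to support patient education, monitoring and disposition planning, so errors for individual patients matter.

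**Working it through.** **The plan's own figure.** The plan gives no number on this point. Its only related calculation is the minimum sample size (item 5): n = P / [(S − 1) ln(1 − R²/S)] with P = 30, R² = 0.11 and S = 0.11/(0.11 + 0.05 × 0.11). With S rounded to 0.952 this gives the stated 5091 patients and 51 events; unrounded it gives 5134. It does not depend on the renal predictor.

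**Inputs from the documents.** Cohort of about 130,000 (Study Population). Event rate of 0.01 over 30 days (item 5), a generic planning rate and not specific to ARF. Together: 130,000 × 0.01 = 1300 events.

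**Assumptions, because the documents give no figures.** Prevalence of the merged predictor q = 10% or 20%. Hazard ratio h = 2 or 4 for patients with GFR <60 who can have the event, against predictor-negative patients. Share f = 1–30% of predictor-positive patients who are on dialysis or in ARF, with relative hazard g.

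**Formulas**

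- Merged hazard ratio ≈ h(1 − f) + g·f. With g = 0 this is h(1 − f).
- Observed/expected in at-risk predictor-positive patients = 1/(1 − f).
- Baseline risk r₀ = 0.01 / [(1 − q) + q(1 − f)h]; predicted risk in ineligible patients = r₀ × h(1 − f).
- Misplaced expected events = 130,000 × q × f × predicted risk.

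**Worked case** (q = 10%, f = 5%, h = 4, g = 0). Merged hazard ratio 4 × 0.95 = 3.80. r₀ = 0.01/(0.90 + 0.38) = 0.78%. Predicted risk for an ineligible patient 3.80 × 0.78% = 2.97%, against a true zero. Ineligible patients 130,000 × 0.10 × 0.05 = 650; misplaced events 650 × 2.97% = 19.3.

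**Range with g = 0** (last two columns span q = 10–20% and h = 2–4)

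| f | HR if h = 2 | HR if h = 4 | Observed/expected, at-risk | Predicted risk, ineligible | Misplaced events of 1300 |
|---|---|---|---|---|---|
| 1% | 1.98 | 3.96 | 1.01 | 1.66–3.06% | 2.3–6.5 |
| 3% | 1.94 | 3.88 | 1.03 | 1.63–3.01% | 6.9–19.2 |
| 5% | 1.90 | 3.80 | 1.05 | 1.61–2.97% | 11.3–31.7 |
| 10% | 1.80 | 3.60 | 1.11 | 1.55–2.86% | 21.7–61.6 |
| 20% | 1.60 | 3.20 | 1.25 | 1.43–2.62% | 39.2–115.6 |
| 30% | 1.40 | 2.80 | 1.43 | 1.30–2.37% | 52.5–160.6 |

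**Check by simulation.** One Cox fit per value of f, with N = 130,000, q = 20% and h = 4, gave a ratio of merged to at-risk hazard ratio of 0.969, 0.897 and 0.798 for f = 3%, 10% and 20%. The formula gives 0.97, 0.90 and 0.80. The standard error of the log hazard ratio was about 0.056, so a 5% bias (ln 0.95 = −0.051) is just under one standard error.

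**If the group can have the event.** With h = 4 and g = 8 the merged hazard ratio rises to 4.12, 4.20 and 4.40 for f = 3%, 5% and 10%. Dilution turns into inflation once g exceeds h.

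These sums treat the renal predictor alone. Other predictors, such as ASA class, may absorb part of the difference in the full model.

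**The case against.** The strongest reply is that the premise rests on a definition that was not available. Appendix 1 holds the ARF criteria. The word new settles the matter for a patient already on dialysis. It does not settle it for preoperative ARF without dialysis: such patients might still meet the event definition, and the bias could then run the other way. This stands, and it limits the claim.

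The reply can add that the size is assumed throughout. The cohort is elective and excludes ASA V, systemic sepsis and ventilator dependence, which plausibly keeps f low, although no figure is given. At f of 1–5% the observed/expected ratio is only 1.01–1.05. This also stands for the GFR <60 effect. It does not remove the error for a dialysis patient, whose predicted risk stays well above zero however small f is.

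A reader might infer several stronger points that the documents do not support:

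- *That the overall ARF risk is materially wrong because the denominator is too large.* With q = 10–20% and f = 5%, 0.5–1% of the cohort is affected, so a risk of 1.00% becomes at most 1.00/0.99 = 1.01%.
- *That excluding preoperative sepsis shows an at-risk rule that was then forgotten for ARF.* The same sentence removes disseminated cancer, wound infection and ventilator dependence, which are not modelled endpoints, and states no such purpose.
- *That missing creatinine would remove the ARF and dialysis flags under the >10% rule.* The plan gives no creatinine missingness and does not say whether the rule applies before or after the components are combined. A composite of this kind is known to be positive whenever either flag is positive.
- *That the other seven models share the error.* The argument about ineligible patients does not apply to them.

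**Conclusion.** The concern holds in a limited form. As written, the ARF model includes patients who cannot have its endpoint: certainly those on preoperative dialysis, and those with preoperative ARF to the extent that Appendix 1 rules them out. It counts them as event-free and assigns them the GFR <60 risk.

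If none of this group can have the event, the GFR <60 hazard ratio is too low by the fraction f: 1–5% for f of 1–5%, and 20–30% only if f is that large. The ineligible patients would be given a risk of about 1.3–3.1% against a true zero, under the assumed q, h and 1% event rate. That is raised relative to 1% overall, but to call it a high risk would overstate it. Neither f nor h is in the documents, and the direction is not established for preoperative ARF without dialysis. The structural point depends on none of these figures: the at-risk set for new ARF is not defined, and the planned checks would not necessarily reveal the consequence.

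**What to change.** For the ARF model only:

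1. Define the risk set as patients who can have new ARF. Exclude those on preoperative dialysis. Exclude those with preoperative ARF if the Appendix 1 definition makes them ineligible; otherwise keep them and enter preoperative ARF as a separate predictor.
2. Use GFR <60 as the renal predictor in that model.
3. Report the number of patients with each component (preoperative ARF, dialysis, GFR <60), so that f is known.

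Splitting the predictor without restricting the risk set would not be enough: it corrects the GFR <60 effect only if that category leaves out the dialysis and ARF patients, and it keeps ineligible patients in the model.

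The cost is a sentence in the protocol and one filter step. The ARF cohort becomes slightly smaller, out of about 130,000, and the model gives no ARF prediction for those excluded. Modelling GFR as continuous with a spline, setting a rule for missing creatinine, and splitting the predictor in the other seven models are options for the investigators and not part of this correction.

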# **Statistical Analysis**

- 1. Preprocessing
  - Convert age from the NSQIP character variable to continuous variable, with Age "90+" recoded as 90
  - Standardizing the coding of missing values: missing coded in NSQIP as "-99", "unknown", "None Assigned", or "NULL". Each variable will be individually examined to ensure that the missing value is correctly standardized.
  - Pre-processing variables for survival analysis: creation of a censored 1 vs. 0 variable for each outcome to be modelled based on time-to-event and the occurrence of complications.
  - Missing values
    - Missing values for candidate predictors will be quantified. If the % missing is:
      - 1. >10% then exclude the predictor from the model
      - 2. <1% then delete (complete case analysis)
      - 3. >=1% and <10% then multiple imputation by chained equations (time-to-event variables are never imputed)
    - Note that patients with missing values for complications will be coded as zero for the complication (i.e. assumed to not have the complication), as the presence of complications would have been in the health records
    - The % missing data for height and weight will be examined in cohort characteristics. If <1% is missing, then BMI will be calculated using these variables.
    - Patients with a complication or adverse event but missing time-toevent data will be excluded from modeling. The extent of bias (i.e. if these patients have different cohort characteristics compared to patients without missing time-to-event data) will be assessed in sensitivity analysis. Note that it is expected for patients without a complication or adverse event to have missing time-to-event data, thus these patients are not excluded.
  - Check collinearity with variance inflation factor and Pearson's correlation coefficient: if present, combine information from collinear variables if feasible (e.g. new variables is "yes" if any of the variables it aggregates are "yes"), otherwise eliminate the variable that has more missing values or would be less accurately ascertained
  - Techniques for class imbalance: e.g. resampling within the derivation set to improve model performance in the case of rare outcomes
- 2. Descriptive statistics

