      - 4. Compare cohort characteristics for patients with a complication or adverse event but missing time-to-event data, vs. patients without missing time-to-event data, to evaluate for the impact of bias from the exclusion of patients with missing time-toevent data
    - Additional analysis will be performed to improve time-to-event predictions, including but limited to:
      - 1. Accelerated failure time (AFT) modeling to directly model failure time. Compared to CPH, APT is more interpretable and robust with omitted predictor variables.
      - 2. Machine learning models that can facilitate time-to-event predictions: including but not limited to boosting trees, neural networks.
- 4. Model evaluation, with bootstrapped 95% confidence intervals and optimism

 Nov 9, 2021
 Protocol Version #2
 Ke et al.
 REB# H21-02670
 5

- AUROC, pseudo R-squared, scaled Brier, calibration plots
- 5. Sample size calculation
  - We used the PMSampsize package in R and followed guidance specifically for time-to-event multivariable modeling (6). Based on an event rate of 0.01 over 30 days (i.e. 0.00033333 per patient per day in the study period totalling 30 days), Cox-Snell R-squared 0.11 (the maximum for the event rate of 0.01 over 30 days) (6), 0.05 acceptable difference in apparent & adjusted R-squared, shrinkage 0.9, a minimum of 51 events (5091 patients, 15,2730 person-days of follow-up) are required for modeling with 30 predictor variables.

Data will be analyzed using R and/or Python.

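### For readmission, the supplied text of sensitivity analysis 2 does not require a complication to precede the outcome, so the analysis can report a predictive gain that no user could obtain

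*Combined protocol and SAP*

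**What the plan says.** The analysis is committed to twice. Candidate predictors has "we will perform sensitivity analysis to determine whether including the occurrence of any major complications", and Statistical Analysis, item 3, sensitivity analysis 2 has "we will perform sensitivity analysis to determine whether including the occurrence of major complications". Both name pneumonia, MI, CVA, VTE, ARF and sepsis, apply to the mortality and readmission models, and ask whether discrimination and calibration get better. Neither gives a timing condition.

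Three other places bear on timing:

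- Model Prediction Endpoints counts complications and adverse outcomes over the same 30 postoperative days, and adds that "time-to-complication date criteria collected from NSQIP variables are included in Appendix 1".
- Methods says the dataset records "whether the patient was diagnosed with major complications (in- or out-of-hospital) as well as the number of postoperative days to the diagnoses of complications".
- Preprocessing states "Patients with a complication or adverse event but missing time-toevent data will be excluded from modeling".

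Performance is to be assessed under "Model evaluation, with bootstrapped 95% confidence intervals and optimism".

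**The concern.** A predictor has to be known when the prediction is made. Patients are often readmitted because of a complication, and the diagnosis may be dated on the day of readmission or shortly after it. If such a diagnosis switches on the predictor, the outcome has helped to create its own predictor.

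The analysis could then conclude that adding complications improves the readmission model when the gain comes from diagnoses that nobody could have had in hand. Predicted risk could also be too high in the patients for whom such a model would be used: those who have had a complication and have not yet been readmitted. The Introduction names monitoring and disposition planning as uses, so this matters in practice.

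**Working it through.** **1. Is there an ordering rule?** The two statements of the analysis name occurrence only. The endpoint section gives one common window. Methods shows that diagnosis days are held, so the order could be enforced. No supplied section specifies a landmark, a time-updated covariate, or a cut-off for predictor information at the readmission date. The plan has no figure of its own on this point to reproduce.

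**2. Hand calculation.** From the documents: n about 130,000. Assumed, because the documents give no rates: readmission r = 0.10, background complication c = 0.03 unrelated to readmission, and a leak fraction q of readmitted patients who acquire a complication date after readmission. With no true effect and one pooled flag:

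- P(flag | readmitted) = c + q(1 - c)
- P(flag | not readmitted) = c
- AUROC of the flag alone = 0.5 + 0.5q(1 - c)
- P(readmitted | flag) = r[c + q(1 - c)] / {r[c + q(1 - c)] + (1 - r)c}

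| q | P(flag given readmitted) | AUROC, flag alone | P(readmitted given flag) |
|---|---|---|---|
| 0% | 0.0300 | 0.500 | 0.0030/0.0300 = 10.0% |
| 2% | 0.0494 | 0.510 | 0.00494/0.03194 = 15.5% |
| 5% | 0.0785 | 0.524 | 0.00785/0.03485 = 22.5% |
| 10% | 0.1270 | 0.549 | 0.0127/0.0397 = 32.0% |

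A simulation at the same r and c gave AUROC 0.500, 0.509, 0.524 and 0.549. The hazard ratio for the fixed flag was 0.98, 1.61, 2.54 and 4.01. Counting the complication only from its diagnosis day returned 0.97-1.02.

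**3. Gain over a baseline model.** A day-by-day simulation used n = 130,000, the same r and c, and one baseline score with AUROC 0.63. Complications fell evenly over the 30 days or early (mean about day 6). Readmission was possible from day 1 or only after discharge. Leaked diagnoses were dated 0-3 days after readmission. Cox models were fitted with and without the complications. The ranges cover this simulation and a repeat on the same assumed rates, with no true effect:

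| Leak | False AUROC gain, full cohort | Gain at day-3 and day-7 landmarks |
|---|---|---|
| 0% | 0.000 | 0.000 |
| 2% | 0.002-0.003 | 0.000 |
| 5% | 0.010-0.012 | 0.000 |
| 10% | 0.029-0.031 | 0.000 |

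**4. Does optimism correction help?** At 0%, 5% and 10% leak, the apparent gain was 0.000, 0.012 and 0.031. The bootstrap-corrected gain was 0.000, 0.011 and 0.031. The correction addresses overfitting, whereas the leak is present in every resample.

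**5. Calibration.** Later readmission by day 30, in patients with a complication by day 7 and not yet readmitted, at 5% leak:

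| True hazard ratio | Predicted | Observed |
|---|---|---|
| 1 | 18-20% | 7-8% |
| 2 | 24-26% | 17-18% |
| 4 | 30-36% | 30-31% |

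**6. Alternative codings, no true effect.** A full-cohort flag for a complication dated before readmission gave hazard ratios of 0.50-0.87, because early readmission leaves less time to have had a prior complication. A time-updated covariate gave about 1.05 when same-day diagnoses were not counted as earlier. When they were counted, it gave 1.6 and 2.1 at 5% and 10% leak.

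**The case against.** The strongest reply is that the text is silent rather than wrong. It nowhere specifies an ever-within-30-days flag, occurrence does not rule out a time-updated covariate, and the plan sends the reader to Appendix 1 for definitions and date criteria. This stands: one can say that the supplied text leaves the order open, not that the plan has no rule.

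A reader might go further and infer from the preprocessing line "creation of a censored 1 vs. 0 variable for each outcome to be modelled based on time-to-event and the occurrence of complications" that occurrence is deliberately set apart from timing. That line describes how outcome variables are built and says nothing on how predictors are coded, so it is not used here. Nor does sensitivity analysis 1 settle the order. Its wording, "we may include complications that tend to happen earlier as predictors for complications that happen later, and may be related to earlier complications", is optional, concerns complications as outcomes, and rests on a general tendency rather than each patient's sequence. It is a separate matter.

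The size is also open to challenge. At 2% leak the false gain is only 0.002-0.003, and no document gives the leak fraction. A reader might infer that the model would always overpredict badly. That does not hold: at 5% leak and a true hazard ratio of 4, prediction is close to observation.

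Finally, landmark models answer a different question from a prediction made at surgery, and they drop early readmissions. That is a real cost, but a complication after surgery cannot be an input to a prediction made at surgery.

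**Conclusion.** The concern holds for the readmission part of sensitivity analysis 2. As worded in the supplied text, complications diagnosed on or after readmission can count as its predictors. The comparison can therefore show better discrimination with no true effect, and the planned optimism correction will not reveal it.

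On the assumed 10% readmission and 3% background complication rates, the false AUROC gain runs from about 0.002 at 2% leak to about 0.031 at 10%. In patients with a complication by day 7 and not yet readmitted, overprediction at 5% leak is large if complications have little true effect, moderate at a hazard ratio of 2 and small at 4. Every rate here is an assumption.

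Two wider readings are not supported. The main models are untouched, because their listed predictors are preoperative or intraoperative. The mechanism also does not carry over directly to mortality, since a complication is not diagnosed after death, and no size is claimed for that model. The conclusion is conditional on Appendix 1 holding no adequate ordering rule.

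**What to change.** In sensitivity analysis 2 for readmission, use the recorded diagnosis days so that only complications known at the time of prediction count:

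- Fit landmark models at prespecified postoperative days, for example 3 and 7. Include patients still free of readmission and count only complications diagnosed by that day.
- Compare AUROC, scaled Brier and calibration with the baseline-predictor model in the same patients.
- Time-updated covariates are acceptable for estimating association if the same-day rule is stated. The full-cohort flag for a complication before readmission should not be used, for the reason in step 6.
- State how a complication without a date is handled in this model. The exclusion in Preprocessing can be read as applying only to the model in which that complication is the outcome.
- If Appendix 1 already has an ordering rule, state it in the analysis text and confirm that it is not the simple full-cohort flag.

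The cost is modest: one extra fit per landmark and model type, on diagnosis days already held. Events are fewer: of about 13,000 assumed readmissions (10% of 130,000), about 11,600-12,900 remain after day 3 and 9,800-11,600 after day 7 in the simulation. Complications after the last landmark go unused, and the question becomes risk from the landmark day rather than from surgery.
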